### **2.3.4 Health Economic Outcomes**

- Hospital length of stay

## **2.4 Eligibility criteria**

Patients are eligible to be included in the trial if they meet the following criteria:

### **2.4.1 Inclusion criteria**

1. Provision of written informed consent (see “2.7 – Informed consent’ for details)
2. Adult patients, undergoing surgical repair of neck of femur fracture
3. Patient can understand and comprehend written and spoken English
4. Patient’s consultee can understand written and spoken English

### **2.4.2 Exclusion criteria**

1. American Society of Anaesthesiologists (ASA) Class I patients
  2. Patients with device-specific exclusions; atrial fibrillation, Raynauds syndrome or disease, peripheral vascular disease, scleroderma, an arteriovenous shunt, valvular heart disease.
- Patients in whom a blood pressure cuff cannot be safely inflated on both arms for any reason (for example, lymphoedema).

4. Patients in whom the treating anaesthetist has judged they will require invasive arterial pressure monitoring.
5. Patients declining consent
6. Patients in whom the treating anaesthetist will use total intravenous anaesthesia (TIVA)
7. Patients in whom there is a >20mmHg difference between non-invasive cuff mean arterial pressure measurements made on opposite arms.

### **2.4.3 The need to recruit patients lacking capacity**

A significant proportion of patients undergoing surgery for hip fracture will lack capacity to consent to involvement in a clinical trial, as a result of pre-existing cognitive dysfunction or acute delirium. These patients are more likely to be comorbid, and may well be at increased risk of developing intraoperative haemodynamic instability, and of developing the complications which have been associated with it. As such, excluding this group of patients would limit the external validity of any findings which could change clinical practice.

Additionally, the intervention is of relatively low burden; it is non-invasive, not painful, and well tolerated in preliminary work and in other trials already published. As such, the burden of taking part is low, and we feel the benefits of producing a trial result which has good generalisability to *all* patients with hip fracture outweigh the burdens of recruiting patients who wouldn't otherwise have capacity.

### **2.4.4 Co-enrolment of patients with other clinical trials**

Where other clinical trials are taking place in the same setting, co-enrolment agreements will be sought. As this is a feasibility study, it will be important to determine whether co-enrolment impacts upon recruitment, and patients who are eligible but not enrolled for this reason.

## **2.5 Participant identification / Screening**

Participants will be identified through daily screening of the 'trauma list' at participating sites by the local research team. Following identification of patients who may be eligible, screening will be carried out by viewing these patient's medical notes to ascertain whether they meet the inclusion criteria, and do not meet any exclusion criteria. If these conditions are met, the patient will be approached by a member of the research team.

Eligibility can be confirmed by any member of the research team who has received appropriate training and has been delegated by the Principle Investigator to do so. This will be confirmed and recorded on a screening proforma prior to randomisation.

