## **2. TRIAL DESIGN**

### **2.1 Trial summary and flow diagram**

This is a feasibility 'before and after' controlled trial, investigating whether it is feasible to conduct a trial testing the hypothesis that the use of continuous non-invasive blood pressure monitoring improves intraoperative haemodynamic stability in patients undergoing repair of fractured neck of femur. The primary endpoint is the proportion of eligible patients who complete the study protocol. Secondary endpoints will include analysis of the effectiveness of patient identification, the reasons for exclusions or failure to complete the study protocol, and an analysis of the incidence of the primary and secondary outcomes planned for the definitive study.

**Figure 1** Trial flow diagram

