### 2.2.2 Secondary objective

Secondary objectives of the trial are to

- Assess the effectiveness of patient identification and screening
- Assess the effectiveness of the blinding
- Identify reasons for failure to recruit patients and screen fails

▪ Explore barriers and facilitators to recruitment

▪ Evaluate the robustness and completeness of data collection.

- Identify the proportion of patients with complete follow up at 30 days
- Identify the incidence of haemodynamic instability by evaluating the nadir blood pressure, the absolute time spent below blood pressure thresholds, and the proportion of anaesthetic time spent with a blood pressure outside defined limits.
- Identify the frequency of occurrence of technical difficulties with the CNAP equipment.
- Identify the incidence of post operative acute kidney injury, myocardial injury, stroke, and death in the post-operative period.

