### 2.2.3 Measures of success

The success of this feasibility trial will be assessed by the trial management group, to consider whether we should apply for funding for a larger, definitive trial. The assessment will be based on the data generated from this feasibility study, and key parameters for assessment will include:

- What is the rate of recruitment
- What is the effectiveness of the process for identifying and screening patients, and what are the reasons for failure to recruit patients if/when this occurs. This will include analysis of reasons patients give for declining consent (if given).
- Are clinicians willing to recruit patients into the study
- Was the CNAP equipment reliable and easy to use?
- Can the CNAP equipment be started by research team and left unattended without any intervention?
- Are the data collection processes during the hospital stay adequate? How complete is the data for the important perioperative parameters?
- What is the rate of follow up of patients at 30 days? What are the reasons for loss of follow-up if any?

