## 2.3 Outcome measures

### 2.3.1 Feasibility Outcomes

- Proportion of eligible patients recruited
- Proportion of recruited patients in whom CNAP was successfully applied and full data collected.
- Proportion of patients with complete in-hospital data set
- Proportion of patients with complete follow up data.

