## **2.7 Informed consent**

### **2.7.1 Consent Considerations**

Patients with hip fractures are typically operated on between 12-48hrs of admission to hospital. Due to the urgent nature of surgical repair, there can be a short time between research staff approaching the patient, and the patient going to theatre. As such, there will be occasions where there is limited time for the patient, or their consultee if they lack capacity, to review the trial documentation and make an informed choice about their participation.

Additionally, owing to the fact patients with hip fracture are in pain, and likely to have received strong analgesia, it is possible they may be finding their time in hospital disorientating and confusing. In the same vein, family and carers may be anxious and distressed by what is going on.

[figure not shown]
As this research will be conducted in the 'emergency setting', it is regulated by the Mental Capacity Act 2005. As patients may lack capacity for the reasons described above, and because of the urgent nature of the treatment limiting access to, and appropriate discussion with Personal Consultees, we will act in accordance with Section 32, subsection 9b of the Mental Capacity Act following a process approved by the relevant research ethics committee.

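### Hip-fracture patients who reach theatre unscreened enter no planned record, so the share identified cannot be estimated and the eligible denominator may be too small

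*Combined protocol and SAP*

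**What the plan says.** **Route in.** Section 2.5: "Participants will be identified through daily screening of the" trauma list, by the local research team. No clock time, number of looks per day, weekend arrangement or second route is given.

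**Time available.** Section 2.7.1: "Patients with hip fractures are typically operated on between 12-48hrs of admission to hospital". It adds that "there can be a short time between research staff approaching the patient, and the patient going to theatre".

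**What the trial wants to learn.** Section 2.1: "Secondary endpoints will include analysis of the effectiveness of patient identification". Section 2.2.2 lists "Assess the effectiveness of patient identification and screening". Section 2.2.3, which guides whether to seek funding for a definitive trial, asks "What is the effectiveness of the process for identifying and screening patients". Section 6.1 also counts screening and identification within the main feasibility outcome.

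**Denominators.** Section 2.1: "The primary endpoint is the proportion of eligible patients who complete the study protocol". The first outcome in 2.3.1 is "Proportion of eligible patients recruited". Neither section says how eligible patients are counted. (The Trial Summary words the primary measure in terms of recruited patients; that wording is not affected.)

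**Records.** A screening proforma confirms eligibility (2.5). A screening log takes patient refusals (2.7.4.1) and consultee declarations and refusals (2.7.5.1). An enrolment log takes verbal consents (2.7.4.1).

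**The concern.** Judging how effective identification was requires a count of the patients who could have been identified, and that count must not depend on the process being judged. The plan has none: proforma, screening log and enrolment log all begin after the research team has found the patient on the trauma list. A patient who is listed and operated on between two looks leaves no trace in any of them.

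Two results are exposed. The share of hip-fracture operations identified has no planned denominator. The proportions of eligible patients recruited and completing the protocol would be too high if eligible patients were missed. The management group could then not tell a low number of eligible patients from a screening process that missed some. Because the design is before-and-after, identification could also differ between the two cohorts without anyone seeing it.

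**Working it through.** The plan states no figure on this point, so there is none to reproduce. The check asks how many patients could meet no screen between admission and surgery.

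**Input from the protocol:** delay D from admission to surgery, 12 to 48 hours (2.7.1).

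**Assumptions (not in the protocol):** D uniform over 12–48 h; one screen every 24 h; the screening times, operating hours and lead times below.

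**Rule.** Let g be the hours from the last usable screen to surgery. A patient is missed when D < g. With D uniform on 12–48, P(missed) = (g − 12)/36 for g from 12 to 48, and 0 for g below 12.

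**Surgery at any hour, admissions even over the day.** P = E[max(0, 24 − D)]/24. The integral of (24 − d) from 12 to 24 is 72, so P = 72/(36 × 24) = 72/864 = 8.3%. If the screen must precede surgery by 2 h, P = 98/864 = 11.3%; by 4 h, 128/864 = 14.8%.

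**Surgery spread evenly over 08:00–18:00.**

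| Screen at | Operations exposed | Mean g | P(missed) |
|---|---|---|---|
| 07:30 | none (g is 0.5 to 10.5 h) | – | 0% |
| 07:30, 2 h lead needed | 08:00–09:30, 15% | 25.25 h | 0.15 × 13.25/36 = 5.5% |
| 12:00 | 08:00–12:00, 40% | 22 h | 0.40 × 10/36 = 11.1% |
| 17:00 | 08:00–17:00, 90% | 19.5 h | 0.90 × 7.5/36 = 18.8% |

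Simulation with 2,000,000 draws gave the same values to within 0.1 percentage point.

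**Effect on the recruited proportion.** Assume 60 eligible patients on record and 30 recruited: 30/60 = 50%. If a share m of eligible patients was missed, the true proportion is 50% × (1 − m): 45.8% at m = 8.3% and 40.6% at m = 18.8%. The trial's records would be identical in all three cases.

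**The case against.** The strongest reply is that a sensible schedule may miss nobody, and that the management group would learn most of what it needs anyway.

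- **Zero misses are possible.** A screen just before a daytime list catches everyone if 12 hours is a firm minimum and no lead time is needed. This stands. But 2.7.1 offers 12 hours only as typical, a 2-hour lead brings the figure to 5.5%, and nothing commits a site to that schedule.
- **Much is still measured.** Refusals are logged, with patients' reasons. Screen failures and reasons for not recruiting are objectives, and losses to co-enrolment are considered in 2.4.4. This stands, so it would be wrong to say that identification cannot be assessed at all or that refusals cannot be separated out. What is missing is the count of patients never screened.
- **Recruitment per unit time is not inflated.** Thirty patients over months 4 to 8 (7.6) already absorbs any misses. This stands.
- **The shift is small against sampling error.** For 30/60 the Wilson 95% interval is about 38% to 62%, and 2.2.3 sets no threshold. This stands too, and limits the point to a modest improvement.

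A reader might infer that half of patients would be missed, since (24 − 12)/24 = 50%. That needs every operation to fall exactly 12 hours after admission, whereas 2.7.1 gives a range up to 48. A reader might also take daily to mean exactly one look per day, or to exclude weekends. The text gives no number of looks, and daily ordinarily includes weekends. Weekday-only screening with seven-day operating would miss (4 × 2 + 42)/168 = 29.8%, but nothing in the protocol says this is intended.

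**Conclusion.** The point holds in a limited form. Followed exactly, the plan yields no estimate of the share of hip-fracture operations that were identified, although it poses that question in three places. The eligible denominators in 2.1 and 2.3.1 may be too small.

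The size cannot be known from the documents. Across assumed daily timings it runs from 0% through about 8% to about 19%. These figures rest on evenly spread delays and on screening and operating hours that the protocol does not state.

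Two further inferences go beyond the text. The screening log is not named as the denominator; the source of the eligible count is simply undefined. Nor do the documents show that missed patients would be out-of-hours cases. Under the assumptions used for surgery at any hour, misses without a lead-time requirement fall on those operated on within 24 hours, but that follows from the assumptions.

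The conclusion rests on the protocol text. The trial flow diagram could not be read in the copy reviewed. If it already plans a count of all operations, what remains is to carry that count into 2.3.1. This is a worthwhile, low-cost improvement and not an analytic error.

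**What to change.** 1. **Section 2.5:** state the time or times of day at which the trauma list is screened and the weekend cover. Require the log to hold every hip-fracture patient screened, not only refusals and declarations.
2. **Section 2.3.1:** add an identification outcome: screened patients who had a repair, divided by all hip-fracture repairs in the site's theatre register over the recruitment period. Use non-identifiable counts from both register and log, each stratified by cohort, day of week, and in or out of hours (defined in advance). One aggregate total would not do, because it cannot show when the missed cases occurred.
3. **Sections 2.1 and 2.3.1:** state the source of the eligible count. Keep recruited/eligible among screened patients and label it so.
4. Report recruited/all operations only as a separate descriptive figure. It includes patients whom 2.4.2 would exclude (for example ASA class I, atrial fibrillation, planned invasive monitoring), so it cannot replace recruited/eligible.

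**Cost:** a small periodic count from existing records, with no patient contact and no change to the 30 patients. The figure against all operations will look less favourable than the one against screened patients.

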## **2.6 Site Staff Training**

Under the supervision of the PI, trained members of the research team will be responsible for identifying potential participants, obtaining consent and conducting study related follow up. Protocol training will be provided to members of the research team by the trial coordinating team at the site on the first visit and throughout the trial, as necessity dictates. This may include device specific training from the manufacturer.

## **2.7 Informed consent**

### **2.7.1 Consent Considerations**

Patients with hip fractures are typically operated on between 12-48hrs of admission to hospital. Due to the urgent nature of surgical repair, there can be a short time between research staff approaching the patient, and the patient going to theatre. As such, there will be occasions where there is limited time for the patient, or their consultee if they lack capacity, to review the trial documentation and make an informed choice about their participation.

Additionally, owing to the fact patients with hip fracture are in pain, and likely to have received strong analgesia, it is possible they may be finding their time in hospital disorientating and confusing. In the same vein, family and carers may be anxious and distressed by what is going on.

[figure not shown]
As this research will be conducted in the 'emergency setting', it is regulated by the Mental Capacity Act 2005. As patients may lack capacity for the reasons described above, and because of the urgent nature of the treatment limiting access to, and appropriate discussion with Personal Consultees, we will act in accordance with Section 32, subsection 9b of the Mental Capacity Act following a process approved by the relevant research ethics committee.

### **2.7.2 Summary of consent process**

We will apply a layered, proportionate approach to consent; patients and consultees will be approached for Verbal Consent prior to surgery using a study summary sheet. Patients and consultees will be approached post-surgery with a full study information sheet where full informed written consent will be sought. If the patient wishes, they can receive full study information before surgery, and provide full informed written consent at this point.

iStabilise Consent Flowchart

patients with hip fracture have a diagnosis of dementia [30] and a third of patients have cognitive dysfunction at the time of admission [31]. Given that this lack of capacity more commonly occurs in those patients who are more likely to have other comorbidities, and thus more likely to come to harm due to intraoperative haemodynamic instability, it is important that these patients are included in the trial; they have the greatest propensity to benefit from improvements in this area, and their exclusion would severely limit the external validity of the study. Additionally, the burden of taking part in the trial is very low (the use of an additional non-invasive monitor which has already been proven equivalent to standard monitoring, in patients who are either under general anaesthetic or often sedated), we do not feel that exclusion of patients without capacity to consent is needed, where a consultee indicates their preferences on the patient's behalf.

### **2.7.3 Assessment of Mental Capacity**

This trial will recruit from a patient population with pre-existing conditions which may affect their capacity of make decisions. It is anticipated that the study population will contain a significant number of patients unable to give informed consent due to lack of capacity.

Members of the research team who will be performing mental capacity assessment and taking consent from patients and or consultees will be trained in mental capacity assessment according to the Mental Capacity Act 2005 and GCP Informed Consent in Adults Lacking Capacity training. An assessment of a patient's mental capacity will be completed before obtaining consent, after the patient is identified as potentially eligible.

### **2.7.4 Patients with capacity**

If a patient has been assessed as having capacity, a delegated member of the research team will discuss participation in the trial. This approach will take place after the patient has undergone the clinical assessments and admissions process as part of their normal clinical care, and has been scheduled for surgery.

#### **2.7.4.1 Verbal consent before surgery**

The research team will provide a verbal description of the trial, as well as a short written summary sheet, allowing the patient adequate and reasonable time to take in the information and ask questions about the trial. At this point, if the patient agrees that they are happy to take part in the trial, the research staff will record the verbal consent on the enrolment log and the summary sheet, and the patient will proceed to treatment allocation. If the patient expresses that they do not want to take part in the study, non-identifiable information will be recorded on the screening log, with details of the reason for declination. There is a full study information sheet that will be available should the patient want to read this before giving verbal consent. The participant will remain free to withdraw agreement at any time up to the time of surgery without giving reasons, and without prejudice to further treatment.

#### **2.7.4.2 Written informed consent after surgery**

The majority of patients who give verbal consent will regain consciousness and be comfortable the day after surgery. At the first available opportunity the research team will visit the patient to discuss the trial in detail and provide a full study information sheet. Patients will be given reasonable and adequate time to consider or raise any questions. If the patient agrees to continue in the study, at this point written informed consent will be obtained. If they choose to withdraw their participation at this point, they are free to do so with no further research follow-up or consequences to their clinical care. Research staff will ask for consent to keep anonymised data already collected as part of

### **2.7.4.3 Written informed consent before surgery**

If the patient has capacity, and wishes to do so, they be provided with full study information before surgery, and if they wish, can provide fully informed written consent. In this situation, no further consent will be required post-surgery.

### **2.7.5 Patients lacking capacity to consent**

If a patient is assessed as lacking capacity to make an informed decision on whether or not to take part in the trial, the site research team will approach a member of the family, a friend or a carer to act as a personal consultee on behalf of the patient. If a personal consultee cannot be found before surgery, the research team will approach a nominated consultee. A nominated consultee can be a registered medical practitioner who is not involved in the organisation or conduct of the research project. The Nominee (independent clinician) must not be the same clinician conducting the consenting process for surgery or anaesthesia. The Consultee (either personal or nominated) will be provided with the relevant information including medical notes and must consider, so far as is reasonably ascertainable

- a. The person's past and present wishes and feelings (and, in particular, any relevant written statement made by them when they had capacity),
- b. The beliefs and values that would be likely to influence their decision if they had capacity, and
- c. The other factors that they would be likely to consider if they were able to do so.

